3. ENDPOINTS AND BASELINE VARIABLES: DEFINITIONS AND CONVENTIONS

3.1. Primary Endpoint(s)

The primary endpoint is incidence of CR/CRi from date of the first dose to the end of treatment per investigator's assessment. See [Appendix 1](#) for definition of CR/CRi.

3.2. Secondary Endpoint(s)

3.2.1. Efficacy

PFS will be defined as the time from date of first dose to the date of disease progression (ie, objective progression, relapse from CR/CRi), or death due to any cause, whichever occurs first. Refer to [Section 6.2.3](#) for details on censoring rules.

OS is defined as the time from date of first dose to the date of death due to any cause. Refer to [Section 6.2.1](#) for details on censoring rules.

Duration of CR/CRi (DoR) based on investigator assessment is defined as the time from date of first response in responders (CR/CRi) to the date of disease progression (ie, objective progression, relapse from CR/CRi, death due to any cause, whichever occurs first (including post-study treatment follow-up disease assessments).

Minimal residual disease (MRD) negativity in participants achieving CR/CRi, ie, MRD negativity, is defined malignant B lymphocytes occurring at a frequency of $<10^{-4}$.

The percentage of patients who achieve MRD-negativity between the date of CR/CRi and end of treatment will be analyzed. The number and percentage of patients with MRD negativity in patients achieving CR/CRi will be summarized descriptively with corresponding two-sided 95% CI. This analysis is based on responders in the safety analysis set.

HSCT rate is defined as the percentage of participants who proceed to HSCT among participants who take at least one dose of inotuzumab ozogamicin.

3.2.2. Safety Endpoints

AEs including SAEs will be graded by the investigator according to the Common Terminology Criteria for Adverse Events (CTCAE) version 5.0 and coded using the Medical Dictionary for Regulatory Activities (MedDRA).

All cases of VOD/SOS irrespective of causality or severity will be reported as SAEs for up to 2 years after the first dose of inotuzumab ozogamicin.

Laboratory abnormalities as characterized by type, severity (as graded by NCI CTCAE v5.0) and timing will be reported.

3.2.3. Pharmacokinetic Endpoints

Pharmacokinetic concentrations: observed maximum serum concentration (C_{max}) after single dose and multiple doses, and observed pre-dose serum concentration (C_{trough}) after multiple doses.

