**Table 3. Pharmacokinetics and ECG Monitoring Flowchart**

Abbreviations. h=hour; PK=pharmacokinetics; ECG=electrocardiogram

- a. PK samples: Consult the laboratory manual for volume of blood needed and sample preparation. To avoid contamination, samples must not be taken from the same lumen that is used for drug infusion. Only in extenuating circumstances may the PK sample(s) be collected from the same lumen. If the same lumen has been used for a PK sample collection it must be documented in the CRF. The actual times may change, but the number of samples will remain the same. All efforts will be made to obtain the samples at the exact nominal time relative to dosing. Collection of samples up to and including 10 hours after dose administration that are obtained within 10% of the nominal time (eg, within 6 minutes of a 60-minute sample) relative to dosing will not be captured as a protocol deviation, as long as the exact time of the collection is noted on the source document and data collection tool (eg, CRF). Collection of samples more than 10 hours after dose administration that are obtained  $\leq$ 1 hour away from the nominal time relative to dosing will not be captured as a protocol deviation, as long as the exact time of the collection is noted on the source document and data collection tool (eg, CRF).
- b. Sample to be drawn before the start of inotuzumab ozogamicin infusion.
- c. Sample to be drawn immediately before end of inotuzumab ozogamicin infusion.
- d. Electrocardiograms (ECGs) are collected in triplicate (3 consecutive ECGs approximately 2 minutes apart) and will be done immediately (within 15 minutes) before each corresponding PK sample collection. Predose ECGs to be performed after premedications and before the start of drug infusion.

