**Figure 1. Study B1931022: Kaplan Meier Curve for Overall Survival (Intent to Treat Population)**

### 2.2.2.1.2. Pharmacokinetic

Based on PK data from 163 patients in Study B1931022, mean peak and trough exposures of inotuzumab ozogamicin increased with each cycle, due to its long steady state elimination half life (12.3 days). Mean peak concentrations in serum were observed at or near the end of infusion with a highest observed mean peak concentration of 308 ng/mL by Cycle 4 Day 1 and the highest observed mean trough concentration of 91.3 ng/mL, by Cycle 4 Day 8, compared to a peak of 211 ng/mL at Cycle 1 Day 1 and a trough of 6.84 ng/mL at Cycle 1 Day 8.

Based on the exposure response analyses of the safety and efficacy data from Phase 3 Study B1931022 and Phase 1/2 Study B1931010, there was a statistically significant ( $p<0.0001$ ) relationship between inotuzumab ozogamicin average serum concentration up to the time of response ( $C_{avg}$ ) and the probability of CR/CRi and MRD negativity. Furthermore, there was a statistically significant ( $p<0.05$ ) relationship between inotuzumab ozogamicin cumulative total serum exposure during Cycle 1 ( $cAUC_{P1}$ ) and the probability of VOD (VOD per assessment of the independent Hepatic Events Adjudication Board (HEAB) for Phase 3 Study B1931022).

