Abbreviations: CR=complete remission; CRi=complete remission with incomplete hematologic recovery.

- a.  $\pm 2$  days (maintain minimum of 6 days between doses).
- b. Dose is based on the patient's body surface area (m^2).
- c. For patients who achieve a CR or a CRi, and/or to allow for recovery from toxicity, the cycle length may be extended up to 28 days (ie, 7-day treatment free interval starting on Day 21).
- d. CR is defined as <5% blasts in the bone marrow and the absence of peripheral blood leukemic blasts, full recovery of peripheral blood counts (platelets  $\geq 100 \times 10^9/L$  and absolute neutrophil counts [ANC]  $\geq 1 \times 10^9/L$ ) and resolution of any extramedullary disease.
- e. CRi is defined as <5% blasts in the bone marrow and the absence of peripheral blood leukemic blasts, incomplete recovery of peripheral blood counts (platelets  $< 100 \times 10^9/L$  and/or ANC  $< 1 \times 10^9/L$ ) and resolution of any extramedullary disease.
- f. 7-day treatment free interval starting on Day 21.

Infusions of inotuzumab ozogamicin must be completed according to time frames specified in the IP manual.

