While doses given within a treatment cycle (ie, Days 8 and/or 15) need not be delayed due to neutropenia or thrombocytopenia, dose delays within a cycle are required for non-hematologic toxicity (see #s 3, 4, 5, 9, and 10 above). Platelet transfusions should be given if

clinically indicated but cannot be used to meet dosing criteria prior to the start of subsequent cycles.

Inotuzumab ozogamicin dosing should be permanently discontinued for any patient with possible, probable or confirmed VOD/SOS or other severe liver toxicity. For inotuzumab ozogamicin, dose delays due to test article-related toxicity  $\leq$  7 days during a treatment cycle are permitted. If dose delay is  $>$  7 days, it will result in omission of the next dose within the cycle; the patient remains eligible to receive the subsequent planned dose assuming all dosing criteria are met. If a dose within a cycle is delayed (ie, Day 8 or 15 dose is delayed), the next dose should also be delayed. A minimum of 6 days should be maintained between doses. Reason for any dose delays must be reported on dosing CRF. If a treatment interruption continues beyond Day 28 of the current cycle, then the day when treatment is restarted will be considered Day 1 of the next cycle. If the beginning of the next cycle is delayed by more than 28 days due to test article-related toxicity/ies (Delay of Day 1 dosing beyond 42 days from prior cycle Day 15 dosing), study treatment will be permanently discontinued unless otherwise agreed by sponsor and investigator. All toxicity grades are according to National Cancer Institute version 5.0 (NCI CTCAE v5.0).

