5.2.10. Nominal and Unscheduled Visits

For all algorithms and analyses, visit labels as specified on the CRF will be used as the nominal timepoint (ie, assessment will not be slotted).

Unless otherwise specified, unscheduled assessments will not be displayed in summary tables by nominal visit/timepoint. Unscheduled assessments will be used when deriving baseline and worst case on-treatment for safety analyses (except where noted for baseline ECGs). Additionally, unscheduled assessments will be used for efficacy analyses (eg, defining date of progression/censoring, best overall response, date of last contact).

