6.2.6. Pharmacokinetic/Pharmacodynamics

Pharmacokinetic concentration analyses will be based on the PK concentration analysis set.

Descriptive summary statistics will be provided for serum concentration at scheduled visits. Serum concentration value below the limit of quantitation will be treated as zero in the descriptive statistics calculation. N, mean, standard deviation, percent coefficient of variation (%CV), median, range, geometric mean and geometric %CV will be presented by cycle, day and nominal time in tabular form.

PK and PD data from this study may be analyzed using compartmental modeling approaches and may also be pooled with data from other studies to investigate any association between inotuzumab ozogamicin exposure and biomarkers or significant safety and/or efficacy endpoints. The results of these modeling analyses, if performed, will be reported separately from the clinical study report.

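### The Cycle 2 Day 1 Ctrough row pools samples taken 7 to 14 days after the last dose and should be shown by actual interval

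*SAP*

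**What the plan says.** SAP 3.2.3 names two PK endpoints, Cmax and the "observed pre-dose serum concentration (C_{trough}) after multiple doses". It does not say how long after the previous dose a trough sample should fall. Under SAP 6.2.6 the summary statistics "will be presented by cycle, day and nominal time in tabular form". SAP 5.2.10 adds that "visit labels as specified on the CRF will be used as the nominal timepoint (ie, assessment will not be slotted"), so a sample keeps its visit label whatever its actual timing.

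Protocol Table 3 schedules a time-0 PK sample at Cycle 2 Day 1, with the instruction "Sample to be drawn before the start of inotuzumab ozogamicin infusion". Doses are planned on Days 1, 8 and 15 of each cycle (Protocol 6.1.1). Cycle 1 is planned at 21 days, but a footnote to Table 8 reads "For patients who achieve a CR or a CRi, and/or to allow for recovery from toxicity, the cycle length may be extended up to 28" (the unit is days). SAP 5.2.4 accordingly gives a nominal length of 21 to 28 days for Cycle 1 and 28 days for all later cycles.

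Protocol 7.1.1.1 also allows doses within a cycle to be omitted and the next cycle to start late.

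**The concern.** A trough is interpretable only with its interval since the last dose. At Cycle 2 Day 1 that interval is set by the length of Cycle 1, which depends on whether the patient has responded or needs time to recover from toxicity. The single Cycle 2 Day 1 row therefore averages two or more different quantities, in proportions linked to outcome. Confirming PK in mainland Chinese patients is a stated purpose of the study, and Ctrough is one of its two PK endpoints. A low Cycle 2 Day 1 mean could reflect many extended cycles rather than any difference in PK, and the planned table could not tell these apart.

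Nothing in the plan catches this. Table 3 counts time from the start of the current infusion, so a pre-dose sample is on time whether the last dose was 7 or 14 days earlier. SAP 5.3.1 allows a concentration to be set to missing for a sampling-time deviation of concern or an anomalous value. That is discretionary, and a permitted cycle extension is neither.

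**Working it through.** **Inputs.** Dosing on Days 1, 8 and 15 (Protocol 6.1.1); cycle lengths (Protocol Table 8, SAP 5.2.4); the delay rule (Protocol 7.1.1.1); pre-dose sampling visits (Protocol Table 3); and, from Protocol 2.2.2.1.2, the Study B1931022 finding that exposures "increased with each cycle, due to its long steady state elimination half life (12.3 days").

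**1. Reproduce the plan's own figure.** The gap from Day 15 to the next Day 1 is cycle length + 1 − 15. For a 28-day cycle this is 28 + 1 − 15 = 14 days. The discontinuation rule begins "If the beginning of the next cycle is delayed by more than 28 days due to test article-related toxicity/ies" and equates that delay with more than 42 days from the prior Day 15 dose. Since 14 + 28 = 42, the formula agrees with the protocol.

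**2. Nominal gap at each pre-dose sample after multiple doses.**

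| Sample | Previous planned dose | Gap (days) |
|---|---|---|
| Cycle 1 Day 15 | Cycle 1 Day 8 | 7 |
| Cycle 2 Day 1 | Cycle 1 Day 15 | 21 + 1 − 15 = 7, up to 28 + 1 − 15 = 14 |
| Cycle 2 Day 8 | Cycle 2 Day 1 | 7 |
| Cycle 4 Day 1 | Cycle 3 Day 15 | 14 |
| Cycle 4 Day 8 | Cycle 4 Day 1 | 7 |

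Only Cycle 2 Day 1 has a range by design. The other visits vary only through visit windows, omissions and delays. Omissions widen the range at Cycle 2 Day 1 too: with the Day 15 dose omitted, the gap is 21 + 1 − 8 = 14 days even for a 21-day Cycle 1.

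**3. Effect for one patient.** Assume mono-exponential decline with a half-life of 12.3 days. The 14-day trough relative to the 7-day trough is 2^(−7/12.3) = 0.674, about 33% lower. Partial extensions lie in between: 0.945 at 8 days, 0.798 at 11 days and 0.713 at 13 days.

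**4. Effect on the row mean.** If a fraction f of patients have the full extension and patients are otherwise alike, the mean relative to an all-7-day row is 1 − f(1 − 0.674).

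| Assumed f | Relative mean | Reduction |
|---|---|---|
| 25% | 0.919 | 8% |
| 50% | 0.837 | 16% |
| 75% | 0.756 | 24% |

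The documents give no value for f, so these figures are illustrative.

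**5. Sensitivity to the half-life.** The 12.3 days is a steady-state value, applied here after one cycle. Assumed half-lives of 4 and 8 days give ratios of 2^(−7/4) = 0.30 and 2^(−7/8) = 0.55. Protocol 2.2.2.1.2 reports a fall from 211 ng/mL (Cycle 1 Day 1 peak) to 6.84 ng/mL (Cycle 1 Day 8 trough), a ratio of 0.032. That includes distribution after a first dose and does not measure decline between days 7 and 14 after the third dose.

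**The case against.** The strongest case against is that this concerns one row of a descriptive table. Timepoints are tabulated separately, so Cycle 2 Day 1 does not contaminate other rows, and there is no pooled Ctrough. SAP 5.2 makes everything except the CR/CRi test descriptive, and no decision rule uses Ctrough. Dose and sample times are recorded (Protocol 6.5 and 8.5), so the interval can be recovered, and compartmental modelling is foreseen. All of this stands and limits the weight of the point. It does not remove it: the modelling is optional and reported outside the clinical study report, and the planned table does not use the recorded times.

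A reader might go further and infer three things that the documents do not support.

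- That all Day 1 troughs are affected. Cycle 4 Day 1 is nominally 14 days for everyone.
- That Ctrough cannot be compared with Study B1931022. The trough values quoted in Protocol 2.2.2.1.2 are Cycle 1 Day 8 (6.84 ng/mL) and Cycle 4 Day 8 (91.3 ng/mL), both nominal 7-day values that do not mix Cycle 1 lengths. No Cycle 2 Day 1 benchmark is given.
- That the Cycle 2 Day 1 mean must fall as more patients respond. The same section reports a positive finding on exposure and response: average concentration up to response was significantly related to the probability of CR/CRi. If responders have higher exposure, this works against the longer interval. Full cancellation of a 14-day gap would need responders' troughs to be 1/0.674 = 1.48 times those of other patients at equal intervals. The documents do not settle whether that is so.

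**Conclusion.** The point holds for Cycle 2 Day 1 only. That row combines troughs taken 7 to 14 days after the last dose, and later with omissions or delays, in proportions tied to response and toxicity. The 33% within-patient difference rests on mono-exponential decline at 12.3 days and a full 7-day extension. It would be larger with a shorter half-life and smaller with a partial extension. The 8, 16 and 24% shifts in the mean also rest on assumed shares of extended patients, and the net direction is not established.

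This is a minor improvement to a descriptive secondary endpoint. The primary test and the sample size are unaffected, and nothing here bears on how patients are dosed.

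**What to change.** In SAP 6.2.6:

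- Derive days since the previous non-zero dose from the recorded dosing and sampling times.
- Present the Cycle 2 Day 1 pre-dose concentration by that interval, for example 5–9 days, 12–16 days and other, alongside the overall row.
- State the expected interval for each remaining trough visit (7 days for Day 8 and Day 15, 14 days for Cycle 4 Day 1) and flag samples outside it.

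Do not restrict Ctrough to 7-day samples. That would discard every on-schedule Cycle 4 Day 1 sample. At Cycle 2 Day 1 it would keep mainly patients whose cycle was not extended, which selects against responders.

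The cost is SAP wording and one derived variable, with no new samples. The downside is smaller numbers per row at Cycle 2 Day 1, where 44 patients at most are divided among the intervals.

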3.2.4. Immunogenicity Endpoints

Incidence of anti-drug antibodies (ADA) and neutralizing antibodies (NAb).

3.3. Exploratory Endpoint(s)

Not applicable.

3.4. Baseline Variables

Start and end dates of study treatment:

The date of first dose (start date) of study treatment is the earliest date of non-zero dosing of the study drug.

The date of last dose of study treatment is the latest date of non-zero dosing of the study drug.

Definition of baseline:

No windowing will be applied when defining baseline.

For efficacy analyses and baseline characteristics associated with tumor assessments, the last assessment prior to the first dose will serve as the baseline assessment.

For safety (including Eastern Cooperative Oncology Group (ECOG) performance status) and immunogenicity the last assessment performed on or prior to date of the first dose of study treatment will serve as the baseline assessment. If there are no observations meeting these criteria, then baseline is considered missing.

Participants who start treatment and discontinue from the treatment on the same day may have two different sets of data collected on study day 1 (one during study and one in the End of Treatment (EOT) visit. Data reported at the EOT visit are not eligible for baseline selection.

Triplicate ECGs are collected; therefore the baseline for each ECG measurement is the average of the pre-dose triplicate measurements reported on during screen period or closest to the start date. Unscheduled assessments will not be included in the calculation of the average. If the last prior to Cycle1/Day 1 ECGs are triplicate ECGs (or only 2), they will be averaged. If the last prior to Cycle1/Day 1 ECG is a single, that will be used as baseline. Baseline heart rate (HR), derived from RR measured in seconds as 60/RR if RR is collected, and QT/QTc interval assessments will be derived from the visit where both HR and QT are not missing. QTcF (Fridericia's correction) and QTcB (Bazett's correction) will be derived based on RR and QT. The average of the replicate measurements will be determined after the derivation of the individual parameters at each timepoint.

3.5. Safety Endpoints

Safety endpoints will be summarized based on the on-treatment period unless otherwise specified.

On-treatment is defined as the time from the first dose of study treatment through minimum (9 weeks after the last administration of the investigational product, start day of new anti-cancer therapy – 1 day). The start date of new anti-cancer therapy after the first dose of study treatment is derived as outlined in [Section 5.2.5](#). Adverse events occurring on the same day as the first dose of study treatment will be considered to have occurred during the on-treatment period. All other assessments which occur on the same day as the first dose of study treatment will be considered baseline assessments (see [Section 3.4](#) for the definition of baseline). If the exact time is collected, the last assessment before the time of first dose of study treatment will be considered as baseline assessments.

Safety data collected outside the on-treatment period as described above will be listed but not summarized.

3.5.1. Adverse Events

Adverse events (AEs) will be coded to preferred term (PT) and system organ class (SOC) using the Medical Dictionary for Regulatory Activities (MedDRA) and classified by severity using the National Cancer Institutes (NCI) Common Terminology Criteria for Adverse Events (CTCAE), version 5.0. For other AEs without specific NCI CTCAE v5.0 definitions, results will be identified according to NCI CTCAE v5.0 “other” categories.

An event will be considered treatment related if the investigator considers so.

An adverse event is considered treatment-emergent relative to a given treatment if the event start date is during the on-treatment period (including on the date of first dose). All cases of VOD/SOS irrespective of causality or severity will be reported as SAEs for up to 2 years after the first dose of inotuzumab ozogamicin.

Adverse Events of Special Interest (AESI)

AEs of special interest (AESI) are as follows:

- GRADE ≥ 3 HEPATOTOXICITY AND/OR SERIOUS HEPATOTOXICITY, INCLUDING VOD/SOS;
- MYELOSUPPRESSION/CYTOPENIA;
- INTERSTITIAL LUNG DISEASE;
- INFLAMMATORY GASTROINTESTINAL EVENT;
- PANCREATITIS;
- SECONDARY PRIMARY MALIGNANCY;

- REPRODUCTIVE AND DEVELOPMENT TOXICITY;
- NEPHROTOXICITY; and
- NEUROTOXICITY.

These events are defined in [Appendix 2](#).

3.5.2. Laboratory Data

Hematology and chemistry result will be programmatically graded according to the NCI CTCAE version 5.0 for relevant parameters. Parameters which cannot be graded will be summarized relative to the normal range (ie, normal range high or normal range low). Additional details are provided in [Section 6.6.3](#).

4. ANALYSIS SETS (POPULATIONS FOR ANALYSIS)

Data for all participants will be assessed to determine if participants meet the criteria for inclusion in each analysis population prior to unblinding and releasing the database and classifications will be documented per standard operating procedures.

Only participants who signed informed consent will be included in the analysis sets below.

Population	Description
Safety	All enrolled participants who receive at least 1 dose of study intervention.
PK concentration	Subset of the safety analysis set and will include participants who have at least one post-dose concentration measurement above the lower limit of quantitation (LLQ) for inotuzumab ozogamicin.
Immunogenicity	Subset of the safety analysis set and will include participants who receive at least 1 dose of investigational product (inotuzumab ozogamicin) and have at least one ADA /NAb sample collected for immunogenicity.

Enrolled: “Enrolled” means a participant's, or their legally authorized representative's, agreement to participate in a clinical study following completion of the informed consent process and assignment to study intervention. A participant will be considered enrolled if the informed consent is not withdrawn prior to participating in any study activity after screening. Potential participants who are screened for the purpose of determining eligibility for the study, but do not participate in the study, are not considered enrolled, unless otherwise specified by the protocol.

